###### Secondary Endpoint(s):

- TTR, DOR and TTP per irRECIST; OS and PFS per irRECIST at 6 and 12 months
- PK parameters for AMG 820 including, but not limited to, maximum observed concentration ( $C_{max}$ ) and minimum observed concentration ( $C_{min}$ ). In addition, area under the concentration-time curve (AUC) and, if feasible, half-life ( $t_{1/2}$ ) for AMG 820.
- CD4, CD8 & CD68 cells number in fresh pre-treatment biopsies

###### Exploratory Endpoint(s):

- Anti-AMG 820 and anti-pembrolizumab antibodies levels
- Biomarker readouts at baseline and treatment related changes
- PK parameters for pembrolizumab include, but are not limited to, concentration at end of pembrolizumab infusion administration, maximum observed concentration ( $C_{max}$ ) and minimum observed concentration ( $C_{min}$ ).

##### 4.2 Planned Covariates and Subgroups

The relationship of covariates to efficacy endpoints will be explored if appropriate. Biomarker data (eg, PD-L1 expression) may be incorporated in additional exploratory subgroup or multivariate analyses. The exploratory analyses of biomarkers may be performed after collection of all samples during the conduct of the study and therefore may be reported after the primary analysis of the safety and efficacy endpoints.

#### 5. Hypotheses and/or Estimations

- AMG 820 in combination with pembrolizumab is safe and well tolerated when administered in subjects with select advanced solid tumors
- AMG 820 can enhance the anti-tumor activity observed with pembrolizumab alone and/or overcome lack of response to pembrolizumab monotherapy in subjects with select advanced solid tumors

## 6. Definitions

### AUC0-last

Area under the concentration-time curve from time 0 to the time of the last quantifiable concentration.

### Baseline

For any variable, unless otherwise specified the baseline is the last assessment taken prior to the first administration of AMG 820. For parameters/assessments not scheduled to be performed (or scheduled but not performed) on the same day as the first administration of AMG 820, the baseline value is the value from the screening period measured closest to the day of first administration of AMG 820.

### Change From Baseline

Change from Baseline is the arithmetic difference between a post-Baseline value and Baseline value:

$$\text{Change (absolute) from Baseline} = (\text{Post-baseline Value} - \text{Baseline Value})$$

$$\text{Change (percent) from Baseline} = [(\text{Post-baseline Value} - \text{Baseline Value}) / \text{Baseline Value}] \times 100$$

### Disease Related Events

Disease Related Events are events (serious or non-serious) anticipated to occur in the study population due to the underlying disease. These could include overall disease progression or pain, or discomfort caused by growing tumors. Such events do not meet the definition of an Adverse Event unless assessed to be more severe than expected for the subject's condition.

**The investigator is responsible for ensuring that all Disease Related Events observed by the investigator or reported by the subject that occur after the first dose of AMG 820 or pembrolizumab through the safety follow-up visit (ie, 135 [+7] days after the last dose of AMG 820 or pembrolizumab, whichever is later) are reported using the Event CRF.**

### Dose Limiting Toxicity

A DLT will be defined as any grade  $\geq 3$  adverse event occurring during a DLT window (21 day period from the initial administration of AMG 820 and pembrolizumab in

combination), and if judged by the investigator to be related to the administration of AMG 820 and/or pembrolizumab.

For details see the Section 6.2.1.2.3 of the protocol.

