6.2.1.2.3 Dose-limiting Toxicity Definition

An adverse event will be considered related to study treatment (possibly, probably, or definitely related to the study treatment) if there is a suspected “reasonable causal relationship” to the study treatment (ICH E2A), and not only a lack of an alternative explanation for the toxicity. All toxicities will be graded using the CTCAE version 4.0 ([Appendix A](#)).

The occurrence of any of the following toxicities during DLT evaluation period (ie, 21 day period from the initial administration of AMG 820 and pembrolizumab in combination) will be considered a DLT, if judged by the investigator to be related to the administration of AMG 820 and/or pembrolizumab:

- Grade 4 non-hematologic toxicity
- Grade 3 or higher pneumonitis
- Grade 3 non-hematologic toxicity lasting > 7 days despite appropriate treatment
 - Grade 3 fatigue will not be classified as DLT, irrespective of duration
- Any grade 3 or higher non-hematologic laboratory value if:
 - medical intervention is required, or
 - the abnormality leads to hospitalization, or
 - the abnormality persists at grade 3 or higher for >1 week unless deemed not clinically important per both investigator and sponsor
- Grade 3 or grade 4 febrile neutropenia

- Grade 3 or higher thrombocytopenia with bleeding and Grade 4 or higher thrombocytopenia lasting > 48 hours or any thrombocytopenia requiring intervention
- Delay in cycle 2 treatment for > 2 weeks due to study drug-related toxicity (unless clearly attributable to pembrolizumab only and delay is caused due to tapering of steroids)
- Any other intolerable toxicity leading to permanent discontinuation of AMG 820 or pembrolizumab

Lymphopenia of any grade is not considered a DLT

Dose limiting toxicities do not include the following:

- A transient (resolving to grade ≤ 1 within 6 hours of onset) grade 3 infusion-related adverse event
- Any grade 3 endocrinopathy that is adequately controlled by hormonal replacement

Cumulative adverse events profile will be taken into consideration when making decisions on dose escalation or de-escalation.

If an AE is clearly attributable to pembrolizumab (based on its known safety profile) and does not exceed the expected severity, this specific AE may be considered exempt from being a DLT.

Disease related events should not be considered a DLT.

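### The one-sentence DLT definition in SAP section 6 conflicts with the protocol criteria it cites, so a DLT table programmed from it could disagree with the DLTs on which the dose was judged

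*SAP*

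**What the plan says.** SAP section 6, under Dose Limiting Toxicity, opens with "A DLT will be defined as any grade" 3 or higher adverse event. It requires onset within 21 days of the first combination dose and an investigator judgment that the event is related to AMG 820 and/or pembrolizumab. It closes with "For details see the Section 6.2.1.2.3 of the protocol". It lists no exceptions and does not say that the protocol prevails.

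Protocol section 6.2.1.2.3 uses the same window and the same relatedness requirement, but gives an itemized list. Among its terms:

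- A duration condition: "Grade 3 non-hematologic toxicity lasting > 7 days despite appropriate treatment".
- Outright exclusions: "Grade 3 fatigue will not be classified as DLT, irrespective of duration"; "Lymphopenia of any grade is not considered a DLT"; "Any grade 3 endocrinopathy that is adequately controlled by hormonal replacement"; and grade 3 infusion-related events that settle within hours.
- Criteria with no minimum grade: any thrombocytopenia that requires intervention, and any other intolerable toxicity that leads to permanent discontinuation of either drug.

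DLT is the first-listed primary endpoint (SAP section 4.1). SAP section 10.5.1.1 plans a summary of DLT incidence and does not restate the criteria. SAP section 10.10 declares one change from the protocol, the removal of RECIST 1.1.

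**The concern.** An SAP definition is what a programmer works from. This one reads as a complete rule, and for a primary endpoint it gives a different set of events from the one the protocol uses to declare the combination tolerable. The mismatch runs both ways: some events would be counted that the protocol rules out, and some protocol DLTs would be left out.

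What is at stake is the agreement between the reported DLT incidence and the dose decision. Part 1 has only 6 to 18 evaluable subjects, and the 6+3 rule in protocol section 3.1.1 turns on one or two events. A clinical study report could then show a DLT count that seems to contradict the conclusion that the dose was tolerable.

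**Working it through.** **1. The plan's own DLT figure.** Both documents state a 47-91% chance of at least one DLT in 6 subjects for a true rate of 10-33%. The formula is 1 - (1 - p)^6.
- p = 0.10: 1 - 0.90^6 = 0.469
- p = 0.33: 1 - 0.67^6 = 0.910

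The figure reproduces. No sample-size statement is wrong; the problem is one of definition.

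**2. The two definitions compared.** Each event is taken to be treatment-related and to occur within 21 days.

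| Event | SAP section 6 | Protocol 6.2.1.2.3 |
|---|---|---|
| Grade 3 fatigue | DLT | Not a DLT |
| Grade 3-4 lymphopenia | DLT | Not a DLT |
| Transient grade 3 infusion-related event | DLT | Not a DLT |
| Grade 3 endocrinopathy controlled by hormones | DLT | Not a DLT |
| Grade 3 non-hematologic event of 7 days or less | DLT | Generally not a DLT, unless it is pneumonitis, a qualifying laboratory value or caught by another item |
| Thrombocytopenia below grade 3 that requires intervention | Not a DLT | DLT |
| Intolerable toxicity below grade 3 that leads to permanent discontinuation | Not a DLT | DLT |

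The first five rows are over-counts by the SAP sentence and the last two are omissions.

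**3. Effect in one cohort.** Suppose 1 of 6 subjects has a protocol DLT. Under protocol section 3.1.1 the combination is tolerable and Part 2 opens. Suppose two other subjects each had a related grade 3 non-hematologic event that resolved within 7 days and met no other item. Counted by the SAP sentence, the table shows 1 + 2 = 3 of 6, which is the count that section 3.1.1 calls non-tolerable.

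**4. Illustration only, on assumed rates.** The documents give no rate for discordant events. Let d be the probability of a protocol DLT and q the probability of another related grade 3 or higher event that is not a protocol DLT. A cohort passes with 0 or 1 DLT in 6, or with 2 in 6 and then 0 in 3. At an assumed d = 0.10:
- 0 of 6: 0.9^6 = 0.5314
- 1 of 6: 6 × 0.1 × 0.9^5 = 0.3543
- 2 of 6, then 0 of 3: 15 × 0.1² × 0.9^4 × 0.9^3 = 0.0717
- P(pass) = 0.957

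Among subjects without a protocol DLT, the chance of a discordant event is r = q/(1 - d). The SAP count reaches 3 or more if at least 3 of 6, at least 2 of 5, or at least 1 of 7 such subjects have one, in the three cases above. At q = 0.10, r = 0.111 and these tail probabilities are 0.0212, 0.0982 and 0.5615. Hence (0.5314 × 0.0212 + 0.3543 × 0.0982 + 0.0717 × 0.5615) / 0.957 = 0.090.

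| q (assumed) | P(SAP count 3 or more, given pass) | P(at least one non-protocol event counted, given pass) |
|---|---|---|
| 0.02 | 1.3% | 12% |
| 0.05 | 3.7% | 28% |
| 0.10 | 9.0% | 49% |
| 0.20 | 24.7% | 76% |

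Protocol section 2.3 describes AMG 820 toxicities, from the earlier study of AMG 820, as mild or moderate in most patients, so the low end is plausible. The model covers over-counting only.

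**The case against.** The best defense is the cross-reference. The SAP entry sends the reader to the right protocol section, SAP section 7.2 takes DLT-evaluability from the protocol, and section 10.10 declares no DLT change. A programmer who follows the reference gets the right table. SAP section 10.5.1 also plans treatment-related event tables and a listing of every adverse event, so a mismatch could be traced. The sponsor has decided to stop investigating the combination (rationale for protocol Amendment 2), which limits the consequences further.

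Most of this stands, and it bounds the point. It does not remove it: details can refine a rule, but they cannot turn an unqualified grade 3 threshold into a list that excludes named grade 3 events and admits lower grades.

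A reader might infer more than the documents support:

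- **That the sponsor redefined DLT, or that dose decisions are affected.** The Dose Level Review Team works from the protocol, and nothing suggests an intended change.
- **That the table will be wrong.** This needs the table to be programmed from the sentence, which cannot be seen here, and a discordant event to occur. Over-counts and omissions could also partly offset.
- **That Hy's Law cases would be missed.** That depends on how multiples of the upper limit of normal map to CTCAE grade, which the documents do not give.
- **That expected pembrolizumab events are a fixed exclusion.** The protocol says only that "this specific AE may be considered exempt from being a DLT", which is discretionary.
- **That a cycle 2 delay of more than 2 weeks cannot fit the 21-day window.** The item can be read as a toxicity arising within 21 days whose delay is established later, so no contradiction is shown.

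**Conclusion.** The point holds as an inconsistency in the definition of a primary endpoint. The SAP sentence is wrong as written: it takes in four kinds of event that the protocol expressly excludes, adds most short-lived grade 3 non-hematologic events, and omits two criteria that have no grade floor. It is best read as faulty shorthand.

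The exposure is limited to the descriptive DLT incidence, and it is conditional on the table following the sentence and on a discordant event occurring. Its size cannot be derived from the documents; the probabilities shown rest wholly on assumed rates. It should be fixed because the endpoint is primary, the numbers are small and the correction is easy. No view is taken on which clinical criterion is right.

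**What to change.** Reconcile the passages. Remove the shorthand sentence from SAP section 6, and state there and in section 10.5.1.1 that DLTs are tabulated by the protocol section 6.2.1.2.3 criteria that the Dose Level Review Team applies.

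The cost is minor SAP wording. Protocol section 9.2.2.1 already has onset and resolution dates, severity, relatedness and action taken recorded for each adverse event. The documents describe no DLT flag, so a few items, such as hormonal control of an endocrinopathy, may need case-by-case classification in the 6 to 18 evaluable Part 1 subjects.

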#### Duration of Response

Duration of response is defined as the number of days between the date of the first tumor assessment indicating an objective response through to the subsequent date of progression as classified by irRECIST or death, or where applicable date of censoring [date of first progressive disease assessment or death or date of censoring – date of the first objective response result +1]. Subjects who respond and have not progressed while on study or died will be censored at the date of the last evaluable radiological assessment. Subjects who do not achieve an objective response will be excluded from the analysis of duration of response.

#### End-of-Study

The EOS is the last planned clinical visit for each subject enrolled in this study.

##### **Primary Completion:**

Defined as when all Study Part 1 and 2 subjects have been enrolled and treated for at least 12 months, been followed up for PFS and OS at 12 months or discontinued from the study.

##### **End of Trial:**

Defined as the time when the last subject is assessed or receives an intervention for evaluation in the study. This is anticipated to occur no sooner than when the last subject enrolled in the study has been followed for at least 12 months after the administration of the first combination dose of study treatment.

#### Enrollment

A subject will be considered enrolled when the investigator decides that the subject has met all eligibility criteria. Enrollment Date is defined as the date collected on the CRF.

#### Investigational Product

The term 'investigational product' is used in to reference to AMG 820 in combination with pembrolizumab.

---

Last Investigational Product Dose Date

The last AMG 820 dose date for each subject is defined as the latest date AMG 820 is administered.

Objective Response as per irRECIST (irOR)

Objective response is defined as a complete response or partial response, as defined by the irRECIST. Confirmation is done by a repeat, consecutive assessment no less than 4 weeks from the date of first documented assessment.

Objective Response Rate as per irRECIST (irORR)

Immune-related ORR (irORR) is defined as the percentage of subjects with irOR.

Overall Survival Time

Overall survival time is calculated as the number of days from the first administration of AMG 820 to death or if applicable censoring [(date of death or censoring – date of first dose of AMG 820 + 1)]. Subjects who withdraw from treatment without withdrawing consent will be followed for survival status up to 12 months.

Subjects who are alive (no record of death) and are lost to follow-up will be censored at the date of last contact.

Progression-Free Survival Time per irRECIST (PFS)

Progression-free survival time is calculated as the number of days from the first administration of AMG 820 to the first assessment of disease progression as per irRECIST or death due to any cause, or if applicable date of censoring (date of progressive disease or death or censoring – first administration of AMG 820 +1).

The following censoring strategies will be used for the progression free survival analysis:

If a subject's disease has not progressed and the subject is alive, progression-free survival time will be censored at the last date they are known to be progression-free (ie, the last evaluable radiological assessment date).

If a subject has no tumor evaluation in the study, progression-free survival time will be censored at the date of the first administration of AMG 820.

Subjects who withdraw consent to participate in the study prior to disease progression will be censored at their last evaluable radiological assessment date.

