7.4 Radiological Imaging Assessment

Radiological imaging to assess the extent of disease will be assessed by standardized contrast-enhanced MRI / CT and evaluated according to Immune-related Response Criteria in Solid tumor irRECIST (ref, [Appendix D](#)). A contrast-enhanced MRI should be the preferred imaging method for tumor staging. A CT should be done when MRI is not possible, is relatively contraindicated (eg, allergy to contrast) or for the evaluation of body sites where MRI is not the recommended adequate staging method. In order to reduce radiation exposure for subjects, low dose CT techniques should be applied whenever possible. Organ-specific imaging protocols or existing diagnostic guidelines should be followed whenever possible to evaluate the full extent of the disease appropriately.

Radiographic imaging of the chest, abdomen and pelvis are required at screening. Tumor assessments must also include all other sites of disease. The screening scans must be performed within 28 days prior to enrollment and will be used as baseline. For NSCLC subjects, MRI of the brain is required at screening. During treatment, follow-up radiographic imaging of the abdomen, pelvis and chest, along with tumor assessments of all other sites of disease, will be performed independent of treatment cycle at week 10 (± 1 week), and then every 10 weeks (± 2 weeks) or more frequently if clinically indicated until confirmed PD per irRECIST or start of new anticancer treatment. Response (immune-related Complete Response [irCR], immune-related Partial Response [irPR]) and progression (immune-related Progressive Disease [irPD]) require confirmation by a repeat, consecutive assessment no less than 4 to 6 weeks from the date of the first documented assessment. For confirming response, the repeat scan may be performed any time after 4 weeks from the first suspected radiologic evidence of response and may be delayed, at the discretion of the managing physician, until the next scheduled scan to avoid unnecessary procedures. Upon discussion with the Sponsor, subjects may continue to receive treatment after radiographic confirmation of progressive disease as long as they continue to derive clinical benefit and until further increase in tumor burden. For analyses purpose, date of PD is the date of initial observed PD.

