### Time to progression per irRECIST (TTP)

Time to progression is calculated as the number of days from the first administration of AMG 820 to the first objective assessment of disease progression as per irRECIST, clinical progression, or if applicable date of censoring (date of progressive disease or censoring – date of first administration of AMG 820 +1). The following censoring strategies will be used:

If a subject's disease has not progressed, time to progression will be censored at the last date they are known to be progression-free (ie, the last evaluable radiological assessment date).

If a subject has no tumor evaluation in the study, time to progression will be censored at the date of the first administration of AMG 820.

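### SAP section 6 counts death as a PFS event, but its rule for subjects with no tumor evaluation censors at first dose without requiring the subject to be alive, and no precedence is stated

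*SAP*

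**What the plan says.** SAP section 6 measures PFS from the first AMG 820 dose "to the first assessment of disease progression as per irRECIST or death due to any cause", or to a censoring date where one applies. It then lists censoring strategies and presents them as the ones the analysis will use. The first covers a subject whose "disease has not progressed and the subject is alive" and censors at the last evaluable radiological assessment. The second is the rule at issue: "If a subject has no tumor evaluation in the study, progression-free survival time will be censored at the date of the first administration". It sets no condition on survival status.

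Neighbouring definitions in section 6 do carry that condition. For overall survival: "Subjects who are alive (no record of death) and are lost to follow-up will be censored at the date of last contact". For duration of response: "Subjects who respond and have not progressed while on study or died will be censored".

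Time to progression (TTP) runs to "the first objective assessment of disease progression as per irRECIST, clinical progression, or if applicable date of censoring". Its rule for a subject with no tumor evaluation is that "time to progression will be censored at the date of the first administration of AMG 820".

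Protocol section 7.4 requires a screening scan as baseline. On-treatment imaging "will be performed independent of treatment cycle at week 10" (plus or minus 1 week), then about every 10 weeks, or sooner if clinically indicated. Protocol section 10.4.3 and SAP section 10.6.2 tabulate Kaplan-Meier PFS at 6 and 12 months with 90% intervals. Protocol section 10 gives neither a PFS definition nor PFS censoring rules.

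**The concern.** A subject who dies before any post-baseline evaluation meets the PFS event definition and also meets a censoring rule, and the two give opposite results. One programmer could count an event on the date of death and another could censor on day 1, each following the SAP. Because the preceding PFS rule and the OS and DOR rules all address death, the omission looks like an oversight and not a deliberate choice.

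Early death is one of the worst outcomes PFS is meant to capture. If it is censored on day 1, the subject leaves the risk set and contributes nothing to the 6- and 12-month estimates tabulated for each group.

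**Working it through.** **Who falls under the rule.** Every subject has a mandatory screening scan, so the phrase about no tumor evaluation has content only if it means post-baseline. The SAP does not say so. On that reading the rule reaches subjects who die, or stop for good, before a first on-treatment evaluation. The back-up scans can miss them. The end-of-treatment scan is asked for only when the last imaging was at least 6 weeks earlier (Protocol 7.4), and the safety-visit scan comes about 135 days after the last dose (Protocol 7.2.3).

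**Deaths before the read time.** Inputs are n subjects in a group and d never-evaluated subjects who die before the read time, with no other censoring before those deaths.

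- Death as event: S = (1 - d/n) x S_rest, where S_rest is the Kaplan-Meier estimate in the other n - d subjects.
- Rule as written: S = S_rest.
- Ratio: 1/(1 - d/n) = n/(n - d).

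| n (maximum group size) | d=1 | d=2 | d=4 |
|---|---|---|---|
| 29 (Groups 2, 4a, 4b) | 1.04 | 1.07 | 1.16 |
| 43 (Group 1) | 1.02 | 1.05 | 1.10 |
| 55 (Group 3) | 1.02 | 1.04 | 1.08 |

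For a group stopped after stage 1, with d=1: n=10 gives 10/9 = 1.11, n=18 gives 18/17 = 1.06, and n=19 gives 19/18 = 1.06.

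In percentage points the shift is S x d/(n - d). For an assumed true 6-month PFS of 10% to 40%:

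- n=29, d=1: 0.4 to 1.4 points
- n=29, d=4: 1.6 to 6.4 points
- n=10, d=1: 1.1 to 4.4 points

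Patient-level illustration: n=29, with 6 subjects assumed event-free at 6 months. With deaths as events, PFS is 6/29 = 20.7% whatever d is. Under the rule as written it is 6/28 = 21.4% (d=1), 6/27 = 22.2% (d=2) or 6/25 = 24.0% (d=4). If 3 further subjects are also censored on day 1, the base becomes 26: 6/26 = 23.1% against 6/25 = 24.0%, 6/24 = 25.0% and 6/22 = 27.3%.

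**Deaths after the read time.** Suppose one of those 6 event-free subjects was never scanned, stayed in survival follow-up and died at month 8. With death as the event, 6-month PFS is 6/29 = 20.7%. Under the rule as written the subject leaves on day 1 and the estimate is 5/28 = 17.9%, which is lower. At 12 months the same subject counts towards d and pushes the estimate up.

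**Size of d.** The documents do not give it, so the values above are assumptions.

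**TTP.** Clinical progression is a stated event. If tumor evaluation means scans alone, a subject with recorded clinical progression and no post-baseline scan is censored at first dose although the event occurred.

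**The case against.** The strongest reply is that the event definition governs. Death from any cause is named as an event, a censoring date is used only where applicable, and the no-evaluation rule merely supplies a date when no last radiological assessment exists. A sensible programmer might read it this way, and then there is no bias. That reading is available, but the SAP does not state it, so the ambiguity stands.

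A reader might infer that 6- and 12-month PFS can only be inflated. The text does not support that. The multiplier holds only for deaths before the read time, and survival follow-up continues after treatment stops (Protocol 7.2.4), so a later death in a never-scanned subject can move the estimate down.

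A reader might also infer that TTP has the same defect. That is weaker. Protocol section 3.1 mentions clinical measurement and clinical evaluation of tumor lesions, so a subject with clinical progression and no scan may still have had a tumor evaluation. Death is not listed as a TTP event, which is a choice of definition.

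It is fair to add that scans at end of treatment, at the safety visit or when clinically indicated reduce d. PFS here is descriptive, with no hypothesis test. The Amendment 2 rationale says the sponsor has decided to stop investigating the combination, so the documents show no development decision that rests on this estimate.

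**Conclusion.** The point holds as an internal contradiction in the SAP's PFS definition. The missing survival condition is certain; whether any reported estimate is biased is not. Bias arises only if the rule is programmed as written, tumor evaluation is taken as post-baseline, and at least one never-evaluated subject dies. It is therefore not a demonstrated error in the results.

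If those conditions hold, one to four such deaths before the read time in a group of 29 raise PFS by a factor of 1.04 to 1.16, assuming no other earlier censoring. Deaths after the read time act in the opposite direction. The effect is confined to secondary PFS estimates. The primary ORR analysis and the Simon decision rules use response, and the OS rule already requires the subject to be alive. The TTP issue is a minor clarification. The PFS wording should be fixed, because a tabulated endpoint should not depend on which of two sentences a programmer follows.

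**What to change.** Amend the PFS rule in SAP section 6 so that day-1 censoring applies only to a subject who has no post-baseline tumor evaluation and no record of death. State that if such a subject has died, the death is a PFS event on the date it occurred. Report by group the number of deaths without a post-baseline evaluation and when they happened.

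For TTP, add a short clarification that a subject with recorded clinical progression and no post-baseline scan is not censored at first dose.

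The cost is two clauses, a few lines of derivation code and one small summary per group. No new data are needed, since dates of death are already required for OS. PFS estimates may change slightly in either direction. There is one trade-off: a never-scanned subject who dies late is treated as progression-free until death, which can overstate PFS. Reporting the timing of these deaths lets the reader judge how far that matters.
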